9.5 Prior and Concomitant Medications

Information regarding prior and concomitant medications, including CF medications, other medications, and herbal and naturopathic remedies, will be collected from each subject’s source documentation for medications taken within 56 days before the Screening Visit through completion of study participation, as defined in [Section 9.1.6](#).

For subjects who are screened but are not subsequently randomized, details of prior medication will be documented only in the subjects’ source documents.

- Subjects should remain on a stable treatment regimen for their CF from 28 days before the Day 1 Visit through completion of study participation. Stable treatment regimen is defined as the current treatment regimen for CF that subjects have been following for at least 28 days before the Day 1 Visit. Subjects should not initiate long-term treatment with new medication from 28 days before the Day 1 Visit through completion of study participation. Guidelines for stable treatment regimens for CF are as follows:
 - o Subjects who are taking inhaled tobramycin or other chronically inhaled antibiotics should remain on that regimen throughout the study.
 - o Subjects who cycle onto and off of an inhaled antibiotic should continue on their prior schedule. The timing of the first dose of study drug on the Day 1 Visit should be synchronized as closely as possible (e.g., not more than ± 3 days) to the first day in the cycle onto the inhaled antibiotic.

- o Subjects who alternate between 2 different inhaled antibiotics should remain on the same cycling schedule during the study. The timing of the first dose of study drug on the Day 1 Visit should be synchronized as closely as possible (e.g., not more than ± 3 days) to the first day in the cycle onto 1 of the inhaled antibiotics.
- Subjects may receive doses of prednisone or prednisolone of up to 10 mg/day chronically, or up to 60 mg daily for up to 5 days.
- Information about bronchodilator use during the study will be collected and documented. Subjects who are using a bronchodilator must have their spirometry assessments performed according to the guidelines provided in [Section 11.6.1](#).

9.6 Administration

9.6.1 Dosing

Study drug will be administered orally. All subjects will receive the same number of tablets each day to maintain the blind. Additional information is provided in the Pharmacy Manual.

Study drug will be administered with a fat-containing meal or snack, such as a standard “CF” meal or snack or a standard meal.

1. It is recommended that the dose be taken within 30 minutes of the start of the meal or snack.
2. Study drug will be administered as 2 fixed-dose combination (FDC) TC or placebo tablets in the morning and as 1 IVA or placebo tablet in the evening. For each subject, doses of study drugs will be taken at approximately the same time (± 2 hours) each day.
3. The date, amount taken, and time of study drug administration, including whether food was taken with each dose, will be recorded for the 2 doses before PK sample collection and the dose received on the morning of PK sample collection.
4. On days of scheduled visits, the morning dose of study drug (TC or placebo) will be administered at the site after predose assessments have been completed. A meal or snack will be provided by the site for the morning dose of TC or placebo.
5. If a subject’s scheduled visit is to occur in the afternoon, the following guidelines must be used:
 - If the dose in the clinic will be within 6 hours of the subject’s scheduled morning dose, the subject should withhold their morning dose of TC or placebo and the morning dose will be administered in the clinic.
 - If the dose in the clinic will be more than 6 hours after the subject’s scheduled morning dose, the subject should take the morning dose of TC or placebo at home.
 - At the Day 1, Day 15, and Week 4 Visits, the morning dose of TC or placebo must be administered in the clinic to enable post-dose ECG assessments or PK sampling (as applicable) relative to the morning dose.
6. Subjects will be instructed to bring all used and unused materials associated with the study drug to the site; study drug will be dispensed at each visit, as appropriate.

9.6.2 Missed Doses

9.6.2.1 Morning Dose of Study Drug

If a subject misses the morning dose of study drug (TC or placebo) and recalls within 6 hours, the subject should take his/her dose with food. If more than 6 hours but fewer than 12 hours have elapsed after his/her usual dosing time, the subject should take the morning dose of TC or placebo but skip the evening dose of study drug (IVA or placebo). If more than 12 hours have elapsed after his/her usual dosing time, the subject should skip the morning dose of TC or placebo and take the evening dose of IVA or placebo.

9.6.2.2 Evening Dose of Study Drug

If a subject misses the evening dose of IVA or placebo and recalls within 6 hours, the subject should take his/her dose with food. If more than 6 hours have elapsed after his/her usual dosing time, the subject should skip that dose and resume his/her normal schedule for the following dose.

9.7 Dose Modification for Toxicity

No dose modifications for toxicity are allowed. Treatment may be interrupted as outlined in Section 9.8. If any unacceptable toxicity arises, individual subjects will discontinue dosing (Section 9.1.4).

9.8 Study Drug Interruption and Stopping Rules

The medical monitor should be notified of an interruption of study drug that lasts >72 hours for any reason and of the resumption of study drug after such interruption.

9.8.1 Liver Function Tests

The central laboratory will notify the medical monitor of ALT or AST $>3 \times$ ULN and total bilirubin $>2 \times$ ULN that are derived from centrally submitted samples.

Subjects with new treatment-emergent ALT or AST elevations of $>3 \times$ ULN, with or without total bilirubin $>2 \times$ ULN, must be followed closely, including confirmatory testing performed by the central laboratory within 48 to 72 hours of the initial finding and subsequent close monitoring of ALT, AST, and bilirubin levels, as clinically indicated.

If a subject cannot return to the site for confirmatory testing, a local laboratory may be used. Local laboratory results must be reported immediately to the medical monitor, and the subject must have the tests repeated and sent to the central laboratory as soon as possible (ideally within 48 to 72 hours).

Study drug administration **must be interrupted** immediately (prior to confirmatory testing) if any of the following criteria are met:

- ALT or AST $>8 \times$ ULN
- ALT or AST $>5 \times$ ULN for more than 2 weeks
- ALT or AST $>3 \times$ ULN, in association with total bilirubin $>2 \times$ ULN and/or clinical jaundice

A thorough investigation of potential causes should be conducted, and the subject should be followed closely for clinical progression.

Study drug administration **must be discontinued** if the following criterion is met:

- Subsequent ALT or AST values confirm the initial elevation that satisfied the interruption rule (above), and no convincing alternative etiology (e.g., acetaminophen use, viral hepatitis, alcohol ingestion) is identified, regardless of whether transaminase levels have improved

All subjects in whom treatment is discontinued for elevated transaminases (and bilirubin, as applicable) should have these levels monitored closely until levels normalize or return to baseline.

If an alternative, reversible cause of transaminase elevation with or without increased bilirubin or clinical jaundice has been identified, study drug administration may be resumed once transaminases return to baseline or are $\leq 2 \times \text{ULN}$, whichever is higher. Regardless of the duration of interruption, the medical monitor should be notified prior to resumption of study drug. Upon resumption of study drug, transaminases and bilirubin should be assessed weekly for 4 weeks. If a protocol-defined transaminase elevation interruption threshold recurs within 4 weeks of rechallenge with the study drug (with confirmation of the initial elevation by repeat testing within 48 to 72 hours), then the study drug must be permanently discontinued, regardless of the presumed etiology.

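### Protocol 9.8.1 lets study drug restart after a liver-related interruption on transaminase recovery alone, even if bilirubin is still above 2 × ULN or jaundice persists

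*Protocol*

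**What the plan says.** Protocol 9.8.1 requires immediate interruption, ahead of confirmatory testing, in three situations: ALT or AST above 8 × ULN; ALT or AST above 5 × ULN for more than 2 weeks; or ALT or AST above 3 × ULN "in association with total bilirubin" above 2 × ULN and/or clinical jaundice. The section then adds: "A thorough investigation of potential causes should be conducted, and the subject should be followed closely for clinical progression". If later values confirm the elevation "and no convincing alternative etiology" is found, study drug must be stopped for good.

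The restart rule covers subjects for whom another cause is found. Where a reversible alternative explanation for raised transaminases "with or without increased bilirubin or clinical jaundice has been identified, study drug administration may be resumed once transaminases return to baseline"; a level of no more than 2 × ULN suffices if baseline is lower. Beforehand, "the medical monitor should be notified prior to resumption of study drug"; afterwards, "transaminases and bilirubin should be assessed weekly for 4 weeks". The section closes with a permanent-stop rule: "If a protocol-defined transaminase elevation interruption threshold recurs within 4 weeks of rechallenge with the study drug", and repeat testing confirms it, "then the study drug must be permanently discontinued, regardless of the presumed etiology".

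Protocol 9.7 allows no dose modification for toxicity, so any restart is at full dose.

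**The concern.** The third interruption trigger has two parts, a transaminase part and a bilirubin-or-jaundice part. The restart rule names the second part, so it was in view when the rule was drafted, yet the only recovery it tests is that of the transaminases. Followed exactly, the rule permits full-dose re-exposure of a subject who is still jaundiced, or whose bilirubin is still above the level that helped to stop dosing.

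The same holds for a subject interrupted on transaminases alone whose bilirubin rises during the interruption: the restart test does not look at it.

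What is at stake is the safety of individual subjects. The trial's inference does not depend on this rule.

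**Working it through.** The plan states no figure here, so there is none to reproduce. The check sets the interruption and restart rules side by side and then works one example.

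**1. Stop rule against restart rule (Protocol 9.8.1, multiples of ULN)**

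| Component | Role in mandatory interruption | Recovery required before restart |
|---|---|---|
| ALT or AST | >8; or >5 for more than 2 weeks; or >3 with raised bilirubin or jaundice | Yes: baseline or ≤2, whichever is higher |
| Total bilirubin | >2, only together with ALT or AST >3 | None stated |
| Clinical jaundice | Only together with ALT or AST >3 | None stated |

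**2. Is the missing condition elsewhere?** Protocol 8.2 excludes total bilirubin ≥2 × ULN, but only at screening. Protocol 9.7, 9.8, 9.9, 11.7.2 and 13.1.1.2 set no bilirubin or jaundice condition for restart, and neither do SAP 9.4.2, 9.4.7.1 and Appendix F. The instruction in 9.8.1 to follow bilirubin until it normalizes or returns to baseline is written for subjects who discontinue treatment.

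**3. Worked example (assumed values).** Baseline ALT is 1.0 × ULN. On drug, ALT is 4.0 and bilirubin 2.5 × ULN, so dosing is interrupted under the third criterion, and a reversible alternative cause is identified.

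- ALT restart ceiling: max(1.0, 2.0) = 2.0 × ULN.
- Later, ALT is 2.0 and bilirubin still 2.5 × ULN. The ALT test is met (2.0 ≤ 2.0), so restart is permitted, with bilirubin 2.5 − 2.0 = 0.5 × ULN above the trigger's own cut-off.
- With a bilirubin condition of ≤2 × ULN, restart would wait (2.5 > 2.0).

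**4. Exposure before the first required test.** With weekly testing, the first test may come about 7 days after restart. Protocol 9.6.1 gives 2 tablets each morning and 1 each evening: 7 × 2 = 14 dosing occasions (7 triple-combination and 7 ivacaftor-only, or matching placebo) and 7 × 3 = 21 tablets.

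**5. Protection after restart.** Starting from ALT 1.0 to 2.0 × ULN, the rise needed to exceed each threshold is:

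- bilirubin >2 × ULN or jaundice present (threshold >3): 3 − 2.0 = 1.0 to 3 − 1.0 = 2.0 × ULN;
- otherwise, threshold >5 sustained for more than 2 weeks: 5 − 2.0 = 3.0 to 5 − 1.0 = 4.0 × ULN;
- otherwise, threshold >8: 8 − 2.0 = 6.0 to 8 − 1.0 = 7.0 × ULN.

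Persistent bilirubin therefore makes the protocol quicker to stop dosing again. Interruption is immediate, and it becomes permanent if the threshold recurs within 4 weeks and is confirmed. Every threshold still needs ALT or AST above at least 3 × ULN, so bilirubin or jaundice that merely persists triggers nothing, before or after restart.

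**6. Effect on the analysis.** SAP 9.4.2 counts subjects with at least one threshold event, and Appendix F has a combined category for ALT or AST >3 × ULN with bilirubin >2 × ULN. The subject in the example is already in that category before restart is considered.

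**The case against.** The strongest reply is that the rule is coherent as it stands. Bilirubin and jaundice only modify a transaminase signal; on their own they never stop dosing. A subject who was never interrupted but has the same current values would stay on drug. Restart also requires an alternative, reversible cause, and the natural reading is that this cause explains the whole presentation, bilirubin included. Restart is optional.

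A reader might infer two stronger things from the gap, and the documents support neither.

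- *That drug may be restarted after an unexplained liver event.* It may not: a confirmed elevation without a convincing alternative cause means mandatory discontinuation, even if transaminases have improved.
- *That bilirubin goes unwatched.* Section 9.8.1 calls for close monitoring of ALT, AST and bilirubin as clinically indicated. The central laboratory alerts the medical monitor to ALT or AST above 3 × ULN and total bilirubin above 2 × ULN. The monitor is told before restart, and a new ALT or AST above 3 × ULN with bilirubin above 2 × ULN or jaundice requires immediate interruption before any confirmation.

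Much of this stands, and it is why the point is minor. It does not remove the point. The cause must be reversible, but it need not have resolved. The medical monitor is notified, with no approval required. The weekly tests and renewed interruption act only after re-exposure. The investigator's and sponsor's power to withdraw a subject (Protocol 9.9), the stop for unacceptable toxicity (9.7) and IDMC review (9.1.7) allow caution without setting a restart condition. The comparison with a never-interrupted subject is also imperfect, since the subject in question has just had a liver event that stopped dosing.

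**Conclusion.** The point holds as a gap in a clinical restart rule: recovery is tested for transaminases and not for bilirubin or jaundice, although these belong to one of the interruption triggers. The safeguards reduce the risk; none makes restart depend on bilirubin or jaundice.

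Its size cannot be put as a rate. The documents give no frequency for such events, so calling them either rare or common would be unsupported. The values in the example are assumptions chosen to show what the text permits. Efficacy conclusions and SAP counts are not materially affected. This is an optional, low-priority improvement.

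**What to change.** In the restart sentence of Protocol 9.8.1, directly after the words on the higher of the two transaminase levels, add: *and total bilirubin is ≤2 × ULN and any clinical jaundice has resolved*. Apply it to every restart under this rule, so that it also covers a subject interrupted on ALT or AST alone whose bilirubin rises afterwards.

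The 2 × ULN cut-off is the one already used in the third interruption criterion and in SAP Appendix F; the sponsor's safety team may prefer a stricter one. Because screening values of 2 × ULN or more are excluded, every eligible subject's screening bilirubin meets it. No new assay is needed: total bilirubin is in the serum chemistry panel with ALT and AST (Protocol Table 11-2).

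The cost is a protocol amendment under Protocol 13.2.3 (agreement of investigator and sponsor, IRB/IEC notification and regulatory submission). Some subjects would restart later, and a subject whose bilirubin stays above 2 × ULN or whose jaundice does not resolve would not restart.

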9.8.2 Rash

Individuals who develop a generalized rash will be monitored closely. Study drug dosing should be interrupted if a subject develops a generalized rash of Grade 3 or higher, or a rash that is considered a serious adverse event. The investigator will notify the medical monitor of any rash that results in interruption of study drug, is Grade 3 or higher ([Section 13.1.1.4](#)), or is a serious adverse event (SAE). Investigators should consider additional evaluation including laboratory testing (e.g., complete blood count [CBC] with differential, LFTs), photographs of the rash, and dermatology consultation. The investigator may consider resumption of study drug if considered clinically appropriate.

9.9 Removal of Subjects

Subjects may withdraw from the study at any time at their own request. Subjects may be withdrawn from study drug treatment at any time at the discretion of the investigator or Vertex for safety, behavior, noncompliance with study procedures, or administrative reasons. If a subject has been withdrawn from study drug treatment, the subject will continue to be followed, provided that the subject has not withdrawn consent (and assent, as applicable).

In addition, a subject must be discontinued from study drug treatment if the subject meets any of the following criteria:

- Has a screening *CFTR* genotype that does not confirm study eligibility if a previous *CFTR* genotype laboratory report was used to establish eligibility. These subjects must be discontinued from the study ([Section 8.1](#))
- Meets any of the stopping (discontinuation) criteria ([Section 9.8](#))
- Becomes pregnant ([Section 11.7.7.2](#))

Subjects who discontinue study drug treatment should return for study assessments, as noted in [Section 9.1.3](#).

If a subject does not return for a scheduled visit, reasonable effort will be made to contact the subject. In any circumstance, reasonable effort will be made to document subject outcome. The investigator will inquire about the reason for withdrawal, request that the subject return all unused investigational product(s), request that the subject return for an ETT Visit and Safety Follow-up Visit, if applicable (see [Section 9.1.3](#)), and follow up with the subject regarding any unresolved AEs.

If the subject withdraws consent or assent for the study, no further assessments will be performed. Vertex may retain and continue using the study data and samples after the study is over, and may use the samples and information in the development of the study compound, and for other drugs and diagnostics, in publications and presentations, and for education purposes. If the subject withdraws from the study, the study data and samples collected will remain part of the study. A subject will not be able to request the withdrawal of his/her information from the study data. A subject may request destruction of the samples collected from him/her during the study as long as those samples can be identified as his/her samples.

9.10 Replacement of Subjects

Subjects who withdraw or are withdrawn before the first dose of study drug on Day 1 may be replaced.

Subjects who withdraw or are withdrawn for nonsafety reasons during the study drug Treatment Period may be replaced at Vertex's discretion.

10 STUDY DRUG INFORMATION AND MANAGEMENT

Study drug refers to VX-445/TEZ/IVA, IVA, and their matching placebos.

10.1 Preparation and Dispensing

Study drug may be dispensed only under the supervision of the investigator or an authorized designee and only for administration to the study subjects.

10.2 Packaging and Labeling

Study drug tablets will be supplied in blister cards by Vertex. Study drug labeling will be in compliance with applicable local and national regulations. Additional details regarding packaging, labeling, and dispensing for study drug will be in the Pharmacy Manual.

10.3 Study Drug Supply, Storage, and Handling

VX-445/TEZ/IVA will be supplied as FDC film-coated tablets containing 100 mg VX-445, 50 mg TEZ, and 75 mg IVA. Matching VX-445/TEZ/IVA placebo tablets will be of similar size and appearance and contain 0 mg VX-445, 0 mg TEZ, and 0 mg IVA ([Table 10-1](#)).

IVA will be supplied as tablets containing 150 mg IVA. Matching IVA placebo tablets will be of similar size and appearance and contain 0 mg IVA ([Table 10-1](#)).

Blister cards must be stored under conditions noted in the Pharmacy Manual. The investigator, or an authorized designee (e.g., a licensed pharmacist), will ensure that all investigational product is stored in a secured area, under recommended storage conditions, and in accordance with applicable regulatory requirements. To ensure adequate records, all study drugs will be accounted for via the drug accountability forms as instructed by Vertex.

Table 10-1 Study Drug: Strength/Dosing Form/Route

Drug Name, Dosing Form, Route	Strength
VX-445/TEZ/IVA, FDC tablet, oral	
VX-445	100 mg
TEZ	50 mg
IVA	75 mg
VX-445/TEZ/IVA-matching placebo, tablet, oral	0 mg
IVA, tablet, oral	150 mg
IVA-matching placebo, tablet, oral	0 mg

FDC: fixed-dose combination; IVA: ivacaftor; TEZ: tezacaftor

10.4 Drug Accountability

The pharmacist or designated study site staff will maintain information regarding the dates and amounts of (1) study drug received; (2) study drug dispensed to the subjects; and (3) study drug returned by the subjects. Subjects will be instructed to return all used and unused materials associated with the study drug to the site. These materials will be retained at the site according to instructions provided by Vertex or its designee. The study monitor will review study drug records and inventory throughout the study.

If a site uses a site-specific drug accountability system and/or process, including processes associated with the destruction of returned materials, the process must be documented and approved by Vertex. The study monitor must review the drug accountability documentation on a regular basis. The study monitor will promptly communicate to Vertex any discrepancies he/she is unable to resolve with the site.

10.5 Disposal, Return, or Retention of Unused Drug

The study site staff or pharmacy personnel will retain all materials returned by the subjects until the study monitor has performed drug accountability. The investigator will ensure that the materials are destroyed in compliance with applicable environmental regulations, institutional policy, and any special instructions provided by Vertex. Destruction will be adequately documented.

10.6 Compliance

To ensure treatment compliance, the investigator or designee will supervise all study drug dosing that occurs at the site. At each visit, site personnel will review that the subject is compliant with study drug dosing and remind the subject of study drug dosing requirements. Compliance will also be assessed by ongoing study drug count.

If a subject demonstrates continued noncompliance of study drug dosing despite educational efforts, the investigator should consider discontinuing the subject from the study.

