9.1.2 Treatment Period

The Treatment Period will be randomized, double-blind, and placebo-controlled. It will last approximately 24 weeks (Day 1 through Week 24). Study drug administration details are provided in [Section 9.6](#).

Randomization will occur before the first dose of study drug during the Treatment Period and may occur on either Day 1 or Day -1. Randomization and stratification details are provided in [Section 9.2](#).

Subjects who prematurely discontinue study drug treatment will remain in the study from the time of discontinuation of study drug treatment through the last scheduled study visit and complete the assessments for all study visits, as described in Section 9.1.3.

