9.1.4 Early Termination of Treatment

If a subject prematurely discontinues study drug treatment, an Early Termination of Treatment (ETT) Visit should be scheduled as soon as possible after the decision to discontinue treatment. Subjects who prematurely discontinue treatment will also be required to complete the Safety Follow-up Visit, approximately 28 days after their last dose of study drug. The assessments performed at the Safety Follow-up Visit are listed in [Table 3-2](#).

If the ETT Visit occurs 3 weeks or later following the last dose of study drug, then the ETT Visit will replace the Safety Follow-up Visit, and a separate Safety Follow-up Visit will not be required.

Subjects who prematurely discontinue study drug treatment will continue to complete all scheduled study visits for assessments following completion of the ETT Visit, as detailed in [Table 3-2](#). Data regarding concomitant antibiotic therapy for sinopulmonary signs/symptoms will also continue to be collected for these subjects.

If a subject withdraws from the study and also withdraws consent or assent, no further assessments will be performed. Vertex may retain and continue to use any data and samples collected before such withdrawal of consent or assent.

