9.1.6 Completion of Study Participation

Completion of study participation for each individual subject is defined as one of the following:

- For subjects who complete the Treatment Period and enter an open-label study within 28 days of the Week 24 Visit: the Week 24 Visit
- For subjects who complete the Treatment Period and do not enter an open-label study within 28 days of the Week 24 Visit: the Safety Follow-up Visit
- For subjects who prematurely discontinue study drug treatment but do not withdraw consent (and assent, as applicable): the latest of the Week 24 Visit, ETT Visit, or Safety Follow-up Visit (if required)
- For subjects who withdraw consent or assent: date of withdrawal of consent or assent, whichever is earlier ([Section 9.9](#))

If subjects are lost to follow-up ([Section 9.1.5](#)), the date of completion of study participation will be defined as the date of the last contact.

The end of study is defined in [Section 13.2.8](#).

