13.1.1.2 Clinically Significant Assessments

Study assessments including laboratory tests, ECGs, PEs, and vital signs will be assessed and those deemed to have clinically-significant worsening from baseline will be documented as an AE. When possible, a clinical diagnosis for the study assessment will be provided, rather than the

abnormal test result alone (e.g., urinary tract infection, anemia). In the absence of a diagnosis, the abnormal study assessment itself will be listed as the AE (e.g., bacteria in urine or decreased hemoglobin).

An abnormal study assessment is considered clinically significant if the subject has 1 or more of the following:

- Concomitant signs or symptoms related to the abnormal study assessment
- Further diagnostic testing or medical/surgical intervention
- A change in the dose of study drug or discontinuation from the study

Repeat testing to determine whether the result is abnormal, in the absence of any of the above criteria, does not necessarily meet clinically significant criteria. The determination of whether the study assessment results are clinically significant will be made by the investigator.

A laboratory value that is Grade 4 will not automatically be an SAE. A Grade 4 laboratory value will be an SAE if the subject's clinical status indicates a life-threatening AE.

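### Protocol 10.6 points investigators to removing persistently noncompliant subjects from the study, whereas the rest of the plan stops drug and keeps the visits

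*Protocol*

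**What the plan says.** Protocol 10.6 (Compliance) deals with subjects whose dosing noncompliance continues despite education. Its instruction is that "the investigator should consider discontinuing the subject from the study".

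The sections that govern stopping drug and follow-up say something different:

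- **9.9 (Removal of Subjects)** allows a subject to be "withdrawn from study drug treatment at any time at the discretion of the investigator or Vertex for safety, behavior, noncompliance with study procedures", among other reasons. It then states: "If a subject has been withdrawn from study drug treatment, the subject will continue to be followed, provided that the subject has not withdrawn consent".
- **9.1.2 (Treatment Period):** "Subjects who prematurely discontinue study drug treatment will remain in the study", through the last scheduled visit.
- **9.1.4 (Early Termination of Treatment):** "Subjects who prematurely discontinue study drug treatment will continue to complete all scheduled study visits for assessments following completion of the ETT Visit". The same section says when assessments end: "If a subject withdraws from the study and also withdraws consent or assent, no further assessments will be performed".
- **9.1.6 (Completion of Study Participation):** "For subjects who prematurely discontinue study drug treatment but do not withdraw consent (and assent, as applicable): the latest of the Week 24 Visit", the ETT Visit or the Safety Follow-up Visit. No category covers a consenting, contactable subject whom the investigator takes out of the study.

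SAP 9.3.1.4 names continued attendance after stopping drug as the means of keeping missing data low. SAP Appendix D lists noncompliance with study drug among the reasons for discontinuing treatment, and places such subjects, if their Week 24 value is missing, in the less favourable of its two missing-data categories.

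**The concern.** The documents treat leaving drug and leaving the study as different events. Protocol 9.9 keeps withdrawal from drug separate from the mandatory study discontinuation of genotype-ineligible subjects, and SAP 9.2.1 tabulates the two kinds of discontinuation separately. A site could therefore take 10.6 at its word and end visits that four other protocol sections assume will continue.

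The data lost could be informative. Persistent noncompliers on active drug plausibly do worse than those who take it, and the FAS analyses subjects as randomized, so their later outcomes belong in the comparison. If those outcomes are missing, the MMRM and the negative binomial model rely on the remaining subjects, and the estimate tends to move in favour of active treatment.

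The endpoints exposed are the through-Week-24 and Week 24 key secondaries. For exacerbations, SAP 9.3.2.1 ends the analysis period of a subject without a Week 24 Visit no later than the end of study participation, so removal also shortens observation. In the SAP text available, the imputation sensitivity analysis covers ppFEV1 only, and runs only if at least 10% are missing at Week 24 in an arm. No counterpart is given for exacerbations, sweat chloride, CFQ-R or BMI. SAP Version 1.1 EUR and Addendum 1, both cited by Addendum 2, could not be identified in that text and might differ.

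**Working it through.** **Inputs from the documents** (Protocol 12.1, SAP 7.2): 180 per arm; 10% dropout, leaving 162; ppFEV1 SD 7 and difference d = 5.0; placebo exacerbation rate 0.6 over 24 weeks; rate ratio 0.60; overdispersion 0.5; two-sided alpha 0.05. The through-Week-24 ppFEV1 average uses five visits (Weeks 4, 8, 12, 16, 24). Day 15 is in the model but not in the average.

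**Assumptions, because the documents give no figure:** a fraction f = 1-5% of the active arm (2-9 of 180) is removed for noncompliance and has no benefit afterwards. Removals on placebo cause no bias. The correlation between visits is 0.5 or 0.7, with compound symmetry for simplicity.

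**Planned power.** Variance of the log rate ratio = (1/0.60 + 1/0.36 + 2 × 0.5)/162 = 0.0336, so SE = 0.183. Power = Φ(0.511/0.183 − 1.96) = 79.6%, which reproduces the stated 80% or so. Removals of 1-5% fit within the 10% dropout already allowed. If they came on top of it, 12% dropout would give 78.7%. Power for ppFEV1 through Week 24 exceeds 99.9% with 162 per arm.

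**ppFEV1 through Week 24.** SE = 7 × √(2/162) = 0.78.

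- Worst case, where the model credits removed subjects with the full effect at every missed visit: bias = f × d × (share of the five visits missed). At a single missed visit this is 0.01 × 5.0 = 0.05 to 0.05 × 5.0 = 0.25.
- If the poor response already shows at the m attended visits (Day 15 included), the MMRM carries most of it forward. The bias left at each missed visit is about f × d × [1 − mρ/(1 + (m − 1)ρ)].

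Example for last visit Week 4, f = 0.05, ρ = 0.5: 0.25 × [1 − 1.0/1.5] × 4/5 = 0.067.

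| Last visit | m | Share missed | Worst case, f = 1% / 5% | Poor response visible, f = 5%, ρ = 0.5 / 0.7 |
|---|---|---|---|---|
| Week 4 | 2 | 4/5 | 0.04 / 0.20 | 0.067 / 0.035 |
| Week 8 | 3 | 3/5 | 0.03 / 0.15 | 0.038 / 0.019 |
| Week 12 | 4 | 2/5 | 0.02 / 0.10 | 0.020 / 0.010 |
| Week 16 | 5 | 1/5 | 0.01 / 0.05 | 0.008 / 0.004 |

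**Exacerbations.** Take a rate ratio of 0.60 in compliers and 1.0 in those removed, with f = 0.05.

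- Everyone followed: 0.95 × 0.60 + 0.05 × 1.0 = 0.620.
- Removed at week w: (0.95 × 24 × 0.60 + 0.05w)/(0.95 × 24 + 0.05w).
  - w = 8: 14.08/23.2 = 0.607
  - w = 12: 14.28/23.4 = 0.610
  - w = 16: 14.48/23.6 = 0.614
- Shift on the log scale: 0.021, 0.016 and 0.010, against an SE of 0.183.
- At f = 0.01: 0.604 with everyone followed, against 0.601, 0.602 and 0.603.

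**The case against.** The best reply is that nothing needs correcting. Section 10.6 belongs to the drug-management chapter and sets no follow-up rule; 9.9 is the section on removal, and it keeps subjects who stop drug in follow-up. Appendix D treats noncompliance as a reason for stopping treatment. The protocol is loose with the phrase elsewhere: 13.1.1.2 lists "A change in the dose of study drug or discontinuation from the study" as a generic action. Harm would need a persistent noncomplier, an investigator who opts for removal, a literal reading, and disregard of 9.9, 9.1.2 and 9.1.4. The removal rate is assumed, and even the worst shifts are a fraction of a standard error. Nor is an amendment entirely free: 13.2.3 requires agreement of investigator and sponsor and submission to regulators.

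Much of this stands. The sentence is discretionary, does not say that visits stop, and may have been meant as stopping drug. The size is hypothetical and small. The limits of the imputation analysis are a separate matter that this edit would not resolve.

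It does not remove the inconsistency. No text gives 9.9 precedence, 10.6 does not refer to it, and 9.9 itself separates drug from study. If stopping drug was meant, the edit simply says so. The paperwork attaches to any protocol change and is no argument for keeping this wording.

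**Conclusion.** The inconsistency is real and its likely effect is small, so this is a low-priority improvement. Under an assumed 1-5% removal from the active arm, the planned 5.0-point effect and no benefit after removal, the through-Week-24 ppFEV1 difference is overstated by 0.01-0.20 points at worst. At 5% removal that falls to 0.004-0.067 if the poor response is already visible at attended visits. The exacerbation rate ratio moves from 0.620 to between 0.607 and 0.614 at 5% removal. A higher removal rate or a larger true effect would scale the ppFEV1 figures up. The Week 4 primary is little affected, because continued noncompliance despite education takes time to establish. Confidence is high that the wording conflicts; how often a site would act on it literally cannot be judged from the documents.

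**What to change.** In Protocol 10.6, have the investigator consider *discontinuing study drug treatment, with scheduled visits continuing per Section 9.1.4 unless consent or assent is withdrawn*, in place of discontinuation from the study. Whether to stop drug stays at the investigator's discretion. The edit closes the option of ending participation for dosing noncompliance alone, which 9.9 does not offer either.

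The cost is one phrase, best carried in the next amendment. Sample size, alpha and visit schedule do not change, and the visits are already required of everyone who stops drug.
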